5.5 Multiple Testing

There is one primary endpoint in our analysis, and no adjustment for multiple testing will be done(26). Thus, our analysis's alpha level for statistical inference will be 0.05, and all p-values will be presented to the third decimal place.

6 Summary of Study Data

Baseline covariates will be summarized and stratified by intervention arm to describe the population . Continuous variables will be summarized using the following descriptive statistics, n (non-missing sample size), mean, standard deviation (SD), medians, interquartile ranges (IQR), minimum and maximum. The frequency and percentages (based on the non-missing sample size) of observed levels will be reported for all categorical measures. In general, all summary tables will be structured with a column for the overall population. Summary tables will also be presented for each treatment and will be annotated with the total population size relevant to that table/treatment. The number of missing observations will be presented in the footnote of each table.

6.1 Subject Disposition

The following CRFs will be used to determine which participants reached the following stages.

Visit (target day)	CRF
Baseline (0)	Enrollment
20 wks	Obstetric ultrasound report
Follow-up	Visit
Delivery	Delivery
Puerperium	Postpartum Visit

6.2 Protocol Deviations

Given that analysis will be by ITT, no specific protocol deviations will impact the approach to analysis. The summary statistics will be produced in accordance with section 5 (General Analysis Considerations).

6.3 Concurrent Illnesses and Medical Conditions

Summary statistics of concurrent illnesses and medical conditions will be produced in accordance with section 5 (General Analysis Considerations).

6.4 Treatment Compliance

Treatment compliance was assessed using the remaining pill count and diary records. Each participant's average compliance rate will be estimated thus:

$$\frac{\text{Number of pills absent from returned regimen sachet}}{\text{Number of pills ever dispensed to participant}} \%$$

The summary statistics will be produced in accordance with section 9.

7 Efficacy Analyses

7.1 Primary Efficacy Analysis – a composite of IUGR, perinatal death or miscarriage

The main analysis will be conducted in the ITT population. The frequency of the primary endpoint will be presented as N and percent of the total study population and by treatment group (LDA vs. placebo). The frequency of the components of the composite endpoint will also be considered.

Log-binomial regression models will be used to evaluate the effect of LDA (vs. placebo) on the occurrence of the composite endpoint, and risk ratios and confidence intervals will be presented. All components of the composite endpoint are included as secondary endpoints, and their analysis is described in 7.2 below. In some cases, the log-binomial models may not converge, and log-Poisson models, which provide consistent but not fully efficient estimates of the relative risk, and its confidence intervals will be used(27).

Baseline covariates that are strongly prognostic of the outcome or imbalanced in the treatment arms may be included in the model if their inclusion improves the precision of the estimates(28,29). Baseline covariates identified from previous studies to be strongly prognostic of the outcome or its components include: maternal age(30–32), hemoglobin genotype(8,33), parity(31), body weight (34–36), educational attainment(37), marital status(35), preeclampsia(31,35), and hemoglobin(38). It is important to note that much of this evidence is from studies in the general population rather than among people with sickle cell disease – and this may impact the extent to which these factors may be prognostic in this study population. The estimates will be regarded as improved if the distance between the upper and lower confidence limits reduces by >10%.

Cluster-robust standard errors from the sandwich package will be employed, clustered on sites.

Table shell 2: Primary composite outcome and components

Outcome	Level	LDA, n(%)	Placebo, n(%)	Risk ratio	Confidence intervals	P-value
IUGR, perinatal death or miscarriage	At least one					
	None					
IUGR	Yes					
	No					
Miscarriage	Yes					

Outcome	Level	LDA, n(%)	Placebo, n(%)	Risk ratio	Confidence intervals	P-value
	No					
Perinatal death	Yes					
	No					

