5.3 Covariates and Subgroups

The following table is a list of covariates to be presented in Table 1, and to be explored for inclusion in models.

Table shell 1. Participant characteristics

Variables	LDA	Placebo	Overall
Age			
Mean (SD)			
Median [IQR]			
Age Categories (years)			
<20			
20 - <30			
30 - <40			
40 and above			
Haemoglobin genotype			
Hb SC			
Hb SS			
Fetal hemoglobin fraction			
<2%			
2 – 10%			
>10%			
Hemoglobin A2 fraction			
<3.5%			
≥3.5%			
Hemoglobin concentration			
Mean (SD)			
Median [IQR]			
Primip			
Yes			
No			
Gestational age at enrollment			
Mean (SD)			
Median [IQR]			
Body weight			
Mean (SD)			
Median [IQR]			
Educational_attainment			

Variables	LDA	Placebo	Overall
No formal education			
Completed Primary			
Completed Secondary			
Completed Tertiary			
Currently in School			
Postgraduate			
Married			
No			
Yes			

Values are n(%) for categorical variables and mean (SD) or median (min, max) for continuous variables. The decision to report the mean (SD) or median (min, max) may be guided by the distribution of the variable based on the Shapiro-Wilk test

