8.3 Prior and Concurrent Medications

The proportion of participants who have used aspirin in the preceding month will be estimated.

9 Sub-group Analyses

The efficacy analyses of LDA on occurrence of the composite outcome (at least one of IUGR, miscarriage, and perinatal death) will be repeated in the following subgroups:

- a) Concurrent medications – hydroxyurea
- b) Hemoglobin genotype – Hb SS vs. Hb SC
- c) Body mass index at ANC enrolment

Subgroup analyses will only be considered if the minimum number of participants in each subgroup is at least 30 people.

10 Reporting Conventions

P-values ≥ 0.001 will be reported to 3 decimal places; p-values less than 0.001 will be reported as “ <0.001 ”. The mean, standard deviation, and any other statistics other than quantiles, will be reported to one decimal place greater than the original data. Quantiles, such as median, or minimum and maximum will use the same number of decimal places as the original data. Estimated parameters, not on the same scale as raw observations (e.g. regression coefficients) will be reported to 3 significant figures.

11 Quality Assurance of Statistical Programming

A second review statistician will independently check the code and output for the entire analyses. To ensure fidelity of results, another statistician will review the analysis based on the codes supplied and by using another statistical software. Stata version 18 (StataCorp, USA) and R-Studio statistical software will be the main statistical software for the analyses. High quality code that is understandable, and reproducible will be produced. Generous annotation and explanations of steps will be performed. Data specifications such as the population of analysis, date and time included, and the description of desired output from analysis will be included.

12 Summary of Changes to the Protocol and/or SAP

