12.1 Adjustments of Statistical Analysis Plan from Protocol

The SAP in the protocol has been revised extensively in this current SAP. Major highlights of the revision include:

- i. This SAP provides more detail on the statistical analysis approach than provided for in the protocol.
- ii. The preferred binomial model for the primary outcome in the protocol was the logistic regression. We now opt for the log-binomial model as this yields risk ratios which are easier to interpret than the odds ratios from logistic regression(40).
- iii. The protocol specified that analysis would be by multivariate regression.
 - a. Multivariate regression is a valid approach for analysing clinical trials with multiple outcomes, as it accounts for any correlation between the outcomes(41,42). We however opt to analyse the multiple components of the composite outcome as a single outcome – this approach is simpler, easier to understand, and could increase the number of events in our study.
 - b. The term “multivariate” is often wrongly used interchangeably with “multivariable”(43). We now remove the term “multivariate”, and instead explain our approach to selecting covariates that we may adjust for in our model.

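### SAP 7.1 chooses the primary model's covariates from the width of the treatment effect's own confidence interval, on an unnamed scale; the effect is small, but the primary model is not pre-specified

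*SAP*

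**What the plan says.** SAP 7.1 fits a log-binomial model for the composite, with a log-Poisson fallback, and "risk ratios and confidence intervals will be presented". On adjustment it says that baseline covariates "strongly prognostic of the outcome or imbalanced in the treatment arms may be included in the model if their inclusion improves the precision" of the estimates, and then gives the test: "The estimates will be regarded as improved if the distance between the upper and lower confidence limits reduces by >10" per cent. It names eight factors from the literature and warns that "this may impact the extent to which these factors may be prognostic in this study population". On variance: "Cluster-robust standard errors from the sandwich package will be employed, clustered on sites".

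Other sections bear on the same choice:
- SAP 5.3 introduces its baseline table with "The following table is a list of covariates to be presented in Table 1, and to be explored for inclusion in models". It lists ten variables. HbF, HbA2 and gestational age at enrolment are in 5.3 but not in 7.1; preeclampsia is in 7.1 but not in 5.3.
- SAP 5.1 places the final analysis on the unblinded, locked dataset. No section describes choosing covariates while blinded.
- SAP 12.1 confirms that selection is intended: having dropped the protocol's term for its regression, the authors "instead explain our approach to selecting covariates that we may adjust for in our model".
- SAP 7.2.1 and 7.2.2 apply the same approach to the secondary endpoints.
- SAP 10 (Reporting Conventions) says "Estimated parameters, not on the same scale as raw observations (e.g. regression coefficients) will be reported to 3 significant figures", which leaves a log-scale interval possible.

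**The concern.** The distance between the limits is a property of the estimated treatment effect, so the rule cannot be applied without outcomes by arm. The model that yields the primary estimate, interval and p-value is then picked by looking at that interval, and the result is reported as if the model had been fixed. Neither entry condition (prognostic or imbalanced) has a cut-off. Nothing says in what order covariates are tried, or which model is primary if several qualify. Two analysts following the SAP faithfully could report different primary results.

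The unnamed scale adds a second problem. A risk-ratio interval gets shorter when the risk ratio itself gets smaller, even if precision is unchanged. The outcome is adverse, so a smaller risk ratio favours aspirin, and the entry test would partly depend on the answer.

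**Working it through.** **Inputs.** 198 women per arm and 20% against 10% risk (SAP 4, stated for IUGR only; no composite rate is given); 15 sites (Protocol synopsis); blocks of four stratified by centre (Protocol 3.4 and 3.6.1); standard errors clustered on site (SAP 7.1). The 198 serves only to set a realistic standard error; whether it delivers its stated power is a separate question.

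**Step 1: the bar on the risk-ratio scale.** With limits RR × exp(±1.96 SE), where SE is the standard error of log RR, width = 2 × RR × sinh(1.96 SE). If adjustment multiplies the RR by k, the rule passes when

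SE(adjusted) < asinh(0.9 × sinh(1.96 × SE) / k) / 1.96.

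At 20% risk in both arms, SE = sqrt(2 × 0.8 / 39.6) = 0.2010 and 0.9 × sinh(0.3940) = 0.3638.

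| Adjusted RR / unadjusted RR | SE needed | Change from 0.2010 |
|---|---|---|
| 0.90 | 0.2010 | 0% |
| 1.00 | 0.1818 | −9.6% |
| 1.10 | 0.1658 | −17.5% |

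At the planned RR of 0.5, SE = sqrt(0.8/39.6 + 0.9/19.8) = 0.2562 and the three changes are 0%, −9.3% and −17.1%. On the log scale, width = 2 × 1.96 × SE, so the bar is a 10% smaller SE whichever way the RR moves.

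**Step 2: what this does to error rates.** The SAP gives no covariate strengths or entry order, so both are assumed. Null trials: 396 women in 15 equal sites, no site effect, 20% risk, log-Poisson model, and the seven factors of 7.1 other than preeclampsia, each with log RR 0.1, 0.2 or 0.3 per SD (the SAP's own warning favours the low end). There were 20,000 trials per setting. Two readings of the rule were used: the best single covariate, or all seven or none.

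Aspirin-side rejections (nominal 2.5%), site-clustered SEs, risk-ratio scale:

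| Model | 0.1 | 0.2 | 0.3 |
|---|---|---|---|
| Unadjusted | 3.32% | 3.35% | 3.54% |
| Fixed seven covariates | 3.55% | 3.52% | 3.57% |
| Rule, best single | 3.48% | 3.86% | 4.41% |
| Rule, all seven or none | 3.73% | 4.18% | 4.86% |
| Best single minus fixed (points) | −0.07 | 0.34 | 0.84 |
| All or none minus fixed (points) | 0.18 | 0.66 | 1.29 |

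The fixed seven-covariate model is the right comparator, because it separates selection from adjustment. The unadjusted rate is already above 2.5% because there are only 15 clusters; that is a separate matter.

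- **How often a covariate enters:** 4 / 15 / 35% of trials (best single) and 11 / 29 / 45% (all or none).
- **Direction:** on the risk-ratio scale, 90 / 88 / 85% and 81 / 75 / 71% of adopted models move towards aspirin. On the log scale, 48–50% do.
- **Two-sided, all or none:** 6.99 / 7.55 / 8.05% (risk-ratio scale) and 6.98 / 7.64 / 8.43% (log scale), against 7.04 / 6.94 / 7.06% for the fixed model. There is no excess at 0.1, and up to 1.0 points (risk ratio) or 1.4 points (log) at 0.3.
- **Ordinary robust SEs:** 97–100% of adoptions move towards aspirin, so the lean is not produced by clustering. The aspirin-side excess over unadjusted falls to 0.0 / 0.1 / 0.2 points (best single) and 0.1 / 0.4 / 0.9 points (all or none).
- **Real precision:** fitting all seven changes the true SD of log RR by +0.2 / −2.4 / −7.2%. In these settings the true gain never reaches 10%, so passing the threshold owes much to chance in the estimated interval.

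**The case against.** Adjusting for prognostic baseline factors is good practice. The factors in 7.1 are cited from the literature, all but preeclampsia are also in 5.3, and 5.3 is a closed list. Inclusion is optional and first requires prognosis or imbalance, gates that the main simulations do not apply. The log scale may be meant, in which case there is no lean. All this is fair, but it does not fix which model is primary.

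Four stronger readings are tempting and should not be drawn:
- *That the rule often flips significance.* It does change the p < 0.05 verdict in some trials, but so does any adjustment. In a repeat of the simulation a fixed seven-covariate model differed from unadjusted in 2.9 / 4.6 / 5.2% of trials, more than the rule did (0.3–1.0% best single, 0.8–2.2% all or none). Verdict changes therefore do not measure selection.
- *That covariates will enter while precision worsens.* The algebra allows it if the RR falls by 15%, but in simulation a fall that large occurred in 0 / 0 / 0.2% of trials for any single covariate and 0.02 / 0.8 / 4.7% for all seven.
- *That the SAP says selection follows unblinding.* It does not say when covariates are chosen. This is inferred from SAP 5.1 and from what the rule needs.
- *That the primary result is biased towards aspirin.* The lean depends on the risk-ratio reading, which is the likelier one because 7.1 and Table shell 2 show no other interval, but it is not stated.

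**Conclusion.** The point stands as a pre-specification weakness of modest size. The absence of a fixed primary model follows from the text alone, and the moving bar on the risk-ratio scale follows from algebra; neither depends on simulation. The error-rate figures do depend on assumed covariate strengths, entry order and a 20% risk. At the weak-covariate end the excess over a fixed model is nil or indistinguishable from nil: for all or none it is 0.18 points, with a Monte Carlo standard error of up to about sqrt(0.029 / 20,000) = 0.12 points, taking the 2.9% verdict disagreement as the bound. The plan should be corrected because the change is easy and removes any question about how the primary model was reached, not because a large bias has been shown.

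**What to change.** In SAP 7.1, and so in 7.2.1 and 7.2.2, delete the 10% width rule and the imbalance trigger. Before unblinding, name one primary model:

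1. treatment plus a short fixed list of baseline covariates, chosen by the sponsor from those already in 5.3 and 7.1, with the unadjusted risk ratio as supportive; or
2. an unadjusted primary model, with that adjusted model as a sensitivity analysis.

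Make 5.3 and 7.1 name the same list. Leave out preeclampsia: it is a secondary endpoint diagnosed after 20 weeks, not a baseline value. Add a sentence such as: *No covariate will be added or removed on the basis of the treatment estimate, its confidence interval or observed imbalance.* Naming the log scale alone would remove the lean but not the selection.

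The cost is SAP wording only; no data collection changes. Option 1 requires an early commitment to a short list: six covariates plus treatment give 198 × (0.20 + 0.10) / 7 = 59.4 / 7, about 8 expected events per parameter if the IUGR planning rates are assumed for the composite. Option 2 gives up a modest precision gain, 0–7% in the simulated settings.

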3.4 Randomisation (Interventions: Investigational and placebo therapy)

This study will employ a randomised, patient and investigator-blinded, multi-centre, parallel-group, placebo controlled design to assess efficacy, safety and tolerability of Low dose aspirin for preventing intrauterine growth restriction and preeclampsia in sickle cell pregnancy (PIPSICKLE).

At the baseline visit, a pregnant woman who is referred or is found to have sickle cell disease (HbSS or HbSC) on routine haemoglobin genotype testing, meets the eligibility criteria and gives informed consent will be enrolled and randomised to one of the two treatments groups (Blinded)

Randomisation and allocation concealment will be done with the use of a web-based randomisation software known as ‘Sealed envelope’ in a 1:1 ratio in blocks stratified according to centre. Only an unblinded pharmacist will be aware of the actual codes and the pharmacist will not be in contact with any of the study participants or investigators.

A total of 476 eligible pregnant HbSS and HbSC women will be randomly assigned to either group.

Those in the LDA group will receive 100mg aspirin daily while those in the placebo group will receive a tablet that looks like the active drug in terms of diameter, thickness and colour.

The drugs will be started between 12 and 28 weeks’ gestation and continued till 36 weeks or delivery, whichever comes earlier.

The study drugs will be prepared in sachets and dispensed in 2 weekly doses (*3 weeks dosage at enrollment*). The women will be sent daily reminders by text message, questioned on compliance at each visit and asked to bring in their used sachets for sighting. All the women will be followed from enrollment till delivery.

The study drugs will be packed in boxes labelled with codes and each box will have sufficient study drugs for one patient for 24 weeks with 4 extra weeks’ worth of drug in case the patient loses some pills. The drug boxes will be delivered to each centre in batches of 8 (4) and 4 (2) more boxes will be sent to the centre whenever a message is received from the centre that there are 4 boxes left.

In the unlikely event that a woman loses all her drugs, the unblinded pharmacist will be asked to label another batch for the woman, based on the code list that she holds. If all the relevant drugs have been used up, the trial pharmaceutical company Emzor Pharmaceutical Ltd, will be asked to produce a new pack of study (investigational or control) drug.

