3.6 Measures to minimize bias

3.6.1 Randomization and allocation concealment.

This will be done remotely by “Sealed envelope”, an on-line randomization service. Sealed envelope will generate a randomization code list and share it ONLY with the unblinded pharmacist, [name], by email. The code list will be in blocks of four and the drugs will be sent out in blocks of four to each site by the unblinded pharmacist. Once the drugs are received by each site, they will let the PI know and she will alert Sealed Envelope so they can load the appropriate codes onto the system. As each new patient is recruited in a particular site, her details are entered into a tablet and a code is generated, which will be one of the codes that were sent to the site. She is then given tablets from the box of drugs that carries the generated code. Only the unblinded pharmacist will have the code list that shows the group that the code is assigned to i.e. whether active drug or placebo.

The number of blocks sent to a site will correspond to the expected recruitment frequency at the site, based on the average number of sickle cell patients seen in the site. So for Alimosho and LASUTH for example, two blocks will be sent initially i.e. 8 packs of drugs, while for Federal Medical Centre, Ebute Metta, one block will be sent i.e. 4 packs of drugs.

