3.3 Randomization and Blinding

At the enrolment visit, any pregnant woman with haemoglobin SS or SC, who meets the eligibility criteria and gives informed consent will be enrolled. Eligible participants will be consecutively enrolled. They will be randomized to one of the two treatment groups. Individual randomization and allocation concealment will be done with the use of a web-based randomization software known as 'Sealed envelope' in a 1:1 ratio in blocks of four. Sealed envelope generated a randomisation code list, shared only with the unblinded pharmacist by email. Each code is pasted on the appropriate drug kit and the drug kits are sent out to each site by the unblinded pharmacist, who is not in contact with any of the site investigators.

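### The primary interval rests on a sandwich clustered on about 15 sites, but SAP 7.1 names no small-sample correction and no reference distribution

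*SAP*

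**What the plan says.** SAP 7.1 fits a log-binomial model to the composite, with log-Poisson if it does not converge, and "risk ratios and confidence intervals will be presented". Its only sentence on variance is "Cluster-robust standard errors from the sandwich package will be employed, clustered on sites". SAP 5.5 sets the standard to be met: the "alpha level for statistical inference will be 0.05". No section gives a correction for the number of clusters, degrees of freedom or a reference distribution.

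The protocol synopsis lists 15 sites; the SAP gives no number. Protocol 3.4 randomises "in a 1:1 ratio in blocks stratified according to centre". SAP 3.3 confirms the unit ("Individual randomization and allocation concealment will be done with the use of a web-based randomization software") and the block size, but does not mention the centre stratum. Protocol 3.6.1 says "The code list will be in blocks of four" and ties supply to expected recruitment: for two example sites "two blocks will be sent initially i.e. 8 packs of drugs", for another "one block will be sent i.e. 4 packs of drugs".

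Centre is in neither the covariate list of SAP 7.1 nor Table shell 1 of SAP 5.3. It enters the primary analysis only as the clustering variable. SAP 7.2 gives models for the secondary endpoints but no variance method. SAP 11 asks for a check in a second statistical package, without fixing a setting on which the two programs should agree.

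**The concern.** A cluster-robust variance is estimated from as many independent pieces as there are clusters. With about 15 it is noisy and tends to be too small. A test statistic built on it behaves roughly like a t on 14 degrees of freedom, not like a normal variable. If the programmer refers it to a normal distribution, the interval is too narrow and the test exceeds its nominal 5%. If the programmer uses t, it does not, or hardly. The SAP leaves that choice open for the headline interval and p-value.

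Two further questions belong with it. The SAP does not say why it clusters when each site holds both arms. And the randomisation stratum is not in the model.

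**Working it through.** The plan gives no figure for this point, so there is none to reproduce. Its sample size matters only as a baseline. At 198 per group and 20% versus 10%, two-sided 5%, z = [0.10·√198 - 1.960·√(2·0.15·0.85)] / √(0.20·0.80 + 0.10·0.90) = (1.407 - 0.990)/0.5 = 0.83, which is 79.8% power. The powers below therefore start near 80% and not at the stated 90%. That is a separate matter.

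**Inputs from the documents.** 15 sites; individual 1:1 randomisation in blocks of four within centre; 396 women (2 × 198); risk 20% versus 10%; alpha 0.05, taken as two-sided because sidedness is not stated.

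**Assumed, because the documents are silent.** Site sizes: equal (six sites of 27, nine of 26), 2:1 (seven of 36, eight of 18), or concentrated (largest site 106 of 396, 27%). Spread of site risk: SD 0-0.4 on the logit. Event risk under the null: 20-30%.

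**Step 1, formula.** Let u be a woman's influence on the log risk ratio: (y - p)/(n·p) for her arm, with a minus sign under placebo. The clustered variance is V = Σ over sites of (sum of u in the site)², optionally multiplied by G/(G-1) = 15/14. The interval is exp(log RR ± c·√V), with c = 1.960 (normal) or 2.145 (t on 14 df).

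**Step 2, approximation.** If the statistic with the factor follows t(14), then P(|t14| > 1.960) = 7.0%. Without the factor the threshold falls to 1.960/√(15/14) = 1.894, and P(|t14| > 1.894) = 7.9%. Between the least and most cautious of these readings the interval on the log scale widens by (2.145/1.960) × √(15/14) = 1.094 × 1.035 = 1.13, or 13%.

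**Step 3, simulation.** 20,000 trials per setting, Monte Carlo standard error 0.15-0.25 points. Two-sided error, nominal 5%:

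| Method | Common effect, equal or 2:1 | Common effect, concentrated | Effect varies (SD 0.3 on log RR), equal or 2:1 |
|---|---|---|---|
| Clustered, normal, no factor | 7.2-8.4% | 10.8-10.9% | not run |
| Clustered, normal, with factor | 6.3-7.4% | 9.7-9.9% | 6.8-7.4% |
| Clustered, t(14), with factor | 4.2-5.2% | 7.4-7.7% | 4.9-5.4% |
| Clustered jackknife, t(14) | 4.5-4.9% | 5.8-5.9% | 4.7-5.0% |
| Site-stratified Mantel-Haenszel | 4.2-5.2% | 4.7-4.9% | 6.6-8.3% |

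An SD of 0.3 puts 95% of sites within a factor exp(1.96 × 0.3) = 1.8 of the average risk ratio. With a larger assumed spread of site risk (intraclass correlation 0.10), the normal reference with the factor gave 7.3% at equal and 7.6% at 2:1 sites.

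**Step 4, consequence for the verdict.** A |z| of 2.145 corresponds to a normal p of 0.032. Trials with a normal-reference p between 0.032 and 0.050 are significant on one reference and not on the other. At 20% versus 10% these are 5.8% of trials with equal sites and 5.6% at 2:1. Under the null they are about 2%.

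**Step 5, power at 20% versus 10%, common effect, equal / 2:1.** Mantel-Haenszel 81.8 / 81.7%; clustered t(14) 75.4 / 75.8%; jackknife t(14) 73.4 / 73.5%. Clustering with a t reference thus costs 6.4 / 5.9 points, or 8.4 / 8.2 with the jackknife. Repeat simulations gave absolute powers about 2 points lower, with a similar gap for clustered t(14).

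**Step 6, leaving centre out.** With individual-level errors that ignore site (risk 20%, site SD 0.4), error was 4.4-4.9% and power 81.1-81.5%. Stratified by site the figures were 4.6-5.1% and 81.3-81.8%. The omission does no visible harm to error or power here.

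**The case against.** The strongest reply is that clustering on site is legitimate. It allows for an aspirin effect that differs between sites, and under strong variation it does better than individual-level errors provided a t reference is used (4.9-5.4% against 6.6-8.3%). That stands. A reader might infer that clustering is a mistake because women, not sites, were randomised; neither the documents nor the figures support this. What is missing is a statement that such variation is the aim, and the details that make the method valid. With a normal reference it fails whether or not the effect varies.

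A second reply is that the software may apply a correction or a t reference unasked. The documents do not settle this. If it applied only G/(G-1), with a normal reference, the error would still be about 6.3-7.4%. If it applied t(14) as well, there would be essentially no excess at equal or 2:1 sites. The finding is therefore that the method is unspecified, not that the SAP prescribes a normal reference.

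A third reply concerns site sizes. The only inequality visible in the documents is 2:1 in initial shipments. The figure near 10% comes from one assumed pattern; another strongly skewed pattern gave 8.0-8.9%, and a 5:1 spread gave 7.3% (both normal reference with the factor). It shows direction and is not a forecast for this trial.

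**Conclusion.** The concern holds as a gap in specification. SAP 7.1 bases the primary interval and p-value on about 15 clusters and leaves open a choice that moves the error of a nominal 5% test from about 5% (t on 14 df with the factor) to 6.3-7.4% (normal with the factor) or 7.2-8.4% (normal without it), at equal or 2:1 sites with a common effect. That the inference is unspecified, and that a normal reference would be too liberal, is well supported. The size is less certain: it rests on assumed site sizes, an assumed reference and an assumed spread between sites. The number of sites that will contribute data is also not given.

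Two stronger inferences should be resisted. Leaving centre out of the model does not cause the narrow intervals; it is a minor point about analysing as randomised. And a site-stratified analysis is not better in every case: it holds 5% for a common effect but not when the effect varies strongly between sites.

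**What to change.** Before unblinding, state the inferential target in SAP 7.1 and adopt one of two coherent options.

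(a) *Inference beyond these sites, or an effect that may vary between them.* Keep the log-binomial model with clustering on site. Name a small-sample correction (jackknife or bias-reduced) and a t reference with degrees of freedom equal to the number of contributing sites minus one. The cost is about 6 to 8 points of power against individual-level errors at equal or 2:1 sites. Under the concentrated pattern even the jackknife left 5.8-5.9% error with a common effect.

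(b) *The effect in the participating sites, or an assumed common effect.* Either add site as a factor to the primary model (log-Poisson with unclustered robust errors, very small sites pooled by number randomised only), or use a site-stratified Mantel-Haenszel risk ratio. Report option (a) as a sensitivity analysis. The cost is error of about 6.6-8.3% if the effect varies with SD 0.3 on the log risk ratio, at equal or 2:1 sites.

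Under (b), replacing the clustering sentence alone is not enough. The log-binomial sentence, the covariate paragraph and the rule on a 10% narrower interval must also be amended, so that 7.1 names a single primary estimator.

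Under either option, state the same variance method in SAP 7.2. The change needs SAP wording and some code, and no change to data or design.
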